### 2.4 Treatment

The 36 women will be randomized to one of the following groups:

1. EGCG daily alone.
2. EGCG daily with clomiphene citrate 100mg for 5 days.
3. EGCG daily with letrozole 5mg for 5 days.

The purpose of studying EGCG in combination with clomiphene citrate or letrozole is to assess the safety of using them together prior to the initiation of the FRIEND study. It is expected that EGCG will decrease fibroid size and decrease humoral activity leading to improved quality of endometrium for implantation. Clomiphene citrate and letrozole are being used for ovulation stimulation as treatment for unexplained infertility. In view of the possibility of interaction and change in toxicity when both are used together for FRIEND study, it was suggested by our pharmacology reviewer to include EGCG with the addition of clomiphene citrate and letrozole for the safety study.

The initial screening visit will include EGCG levels, liver function, folate and estrogen levels. A genetics sample collection, urine pregnancy test and pelvic ultrasound will also be performed after informed consent. Patient will be given the EGCG (Green Tea extract) to start after the screening visit. Patients will be counseled on dietary restrictions while on EGCG.

Visit 1 will occur on menstrual cycle day  $3 \pm 2$  days. EGCG levels over 8 hours, liver function, and urine pregnancy testing will occur at this visit. Patients will be assigned into their groups and provided with their respective treatments at this visit.

Patient will return between days 8-10 of the cycle for Visit 2. EGCG levels over 8 hours, liver function, estrogen, and urine pregnancy testing will occur at this visit.

The patient will return for Visit 3 between days 14-16 for a pelvic ultrasound evaluation of endometrial thickness and ovarian characteristics.

The final study visit (Visit 4) will be approximately 4 weeks after initiation of the study treatment and will involve EGCG levels, liver function, folate, and urine pregnancy test and pill counts.

The 4 lab panels (screening, Visits 1, 2, and 4) will include EGCG and metabolite analyses, liver panel (AST, ALT, total bilirubin, ALP) and estrogen levels, and a urine pregnancy test. The EGCG analyses at visits 1 and 2 will include testing over 8 hours.

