#### 4.3.3 Study Summary

Recruitment and Prescreening: see Section 5 descriptions following.

Screening visit (anytime in cycle 1):

1. Obtain informed, signed consent.
2. Complete medical/gynecological/menstrual history and physical exam of female study participant.
  - Vital signs, height, weight, hip and abdominal circumference, BMI
  - Pap smear if necessary per current ACOG time-frame guidelines
  - Standard pelvic and breast exam conducted by physician or within past 12 months
3. Perform radiological exams.
  - Pelvic ultrasound measuring uterine and ovarian characteristics or within past 3 months
4. Laboratory tests: EGCG and metabolites, liver function, folate, estrogen levels, genetics sample collection and urine pregnancy test.
5. Dispense Green Tea extract and educate on dietary restrictions while taking Green Tea extract and with the importance of taking food. All patients to start Green Tea extract at this visit.
6. Contraception education. Patients will be counseled to use non-hormonal double-barrier method: a male/female condom plus spermicidal agents, cervical cap, diaphragm or sponge.
7. Concomitant medication collection.

Visit 1 (Day 1-5):

Patient will be seen on menstrual cycle day  $3 \pm 2$  days for clomiphene citrate/letrozole initiation visit

1. Vital signs and weight.
2. Laboratory tests: EGCG levels over 8 hours (0.5,1,2,4,6,8), liver function, folate, estrogen level, and urine pregnancy testing.
3. Concomitant medication collection and pill counts of EGCG.
4. Randomization and dispensation of clomiphene citrate/letrozole.
5. Contraception education. Patients will be counseled to use non-hormonal double-barrier method: a male/female condom plus spermicidal agents, cervical cap, diaphragm or sponge.

Visit 2 (day 8-10):

Patient will return several days after final clomiphene citrate/letrozole administration

1. Vital signs and weight.
2. Laboratory tests: EGCG levels over 8 hours (0.5,1,2,4,6,8), liver function, folate, estrogen level and urine pregnancy testing.

3. Concomitant medication collection and pill counts of EGCG and clomiphene citrate or letrozole as appropriate.
4. Contraception education. Patients will be counseled to use non-hormonal double-barrier method: a male/female condom plus spermicidal agents, cervical cap, diaphragm or sponge.

Visit 3 (day 14-16):

1. Pelvic ultrasound via a transvaginal probe or transabdominal transducer evaluation of endometrial thickness and ovarian characteristics.

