## 5.7 Transvaginal Ultrasound Exam

An ultrasound exam will be performed with a transvaginal probe. For subjects who cannot tolerate a transvaginal probe, a transabdominal ultrasound evaluation will be performed. The following measures will be obtained at screening: uterine dimensions, leiomyoma presence and size, other uterine abnormalities, endometrial thickness, ovarian size in three dimensions, the size of the largest ovarian follicle, follicle count in the largest plane and ovarian morphology. Ovarian size is determined by measuring the largest plane of the ovary in two dimensions and then turning the vaginal probe 90 degrees and obtaining a third measurement. Endometrial thickness is the largest anterior-posterior measurement of the endometrium in the sagittal plane. Ovarian volume is determined by the formula for a prolate ellipsoid (length x width x height x  $\pi/6$ )(Pache, Hop et al. 1991). If the patient has had no prior test of tubal patency, this may be the desired time to perform a sonohysterogram to determine tubal patency. Only endometrial thickness and ovarian follicular measurements will be measured at visit 2.

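### Section 5.7 puts the follow-up endometrial and follicle scan at Visit 2 (day 8-10); sections 2.4 and 4.3.3 put it at Visit 3 (day 14-16)

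*Combined protocol and SAP*

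**What the plan says.** Section 5.7 lists what the screening scan records, beginning: "The following measures will be obtained at screening: uterine dimensions, leiomyoma presence and size, other uterine abnormalities, endometrial thickness". It then deals with follow-up in one sentence: "Only endometrial thickness and ovarian follicular measurements will be measured at visit 2". It mentions no scan at Visit 3.

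Section 2.4 sets Visit 2 at cycle days 8-10 and gives its content as: "EGCG levels over 8 hours, liver function, estrogen, and urine pregnancy testing will occur at this visit". It then says: "The patient will return for Visit 3 between days 14-16 for a pelvic ultrasound evaluation of endometrial thickness and ovarian characteristics".

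Section 4.3.3 agrees. Its Visit 2 list (day 8-10) has four items: vital signs and weight, laboratory tests, medication and pill counts, and contraception education. Its Visit 3 list (day 14-16) has one item: "Pelvic ultrasound via a transvaginal probe or transabdominal transducer evaluation of endometrial thickness and ovarian characteristics".

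For the baseline scan, section 4.3.3 allows the screening visit at any time in cycle 1 and describes the scan as: "Pelvic ultrasound measuring uterine and ovarian characteristics or within past 3 months". Randomization follows at Visit 1.

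Sections 2.6 and 6.3 make between-arm changes in endometrial thickness and ovarian characteristics a secondary outcome. Sections 2.7 and 6.4 plan descriptive summaries of the changes, and a two-way ANOVA on treatment and fibroid status for comparison.

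**The concern.** The section a sonographer would consult for the scan gives a visit that the two visit-by-visit schedules contradict. The timing matters because the outcome is a response to a 5-day course of clomiphene or letrozole. Visit 1, where the drug is dispensed, falls on day 3 ± 2. If dosing starts on day 5, the last dose is on day 9, so a day 8-10 scan could fall during dosing or within a day of its end. If some of the four sites followed 5.7 and others 4.3.3, scans from two phases of the cycle would be pooled in a trial of 36 women.

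The second question is what the follow-up scan is compared with. The screening scan is the only pre-treatment scan, so it is the baseline for any change. Because it may be taken on any day of cycle 1, or be up to three months old, part of each woman's change may reflect where she was in her cycle at screening. That makes within-arm change hard to interpret and may add noise to the comparison of arms.

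**Working it through.** **Visit number.** The sections side by side:

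| Section | Visit 2 | Visit 3 |
|---|---|---|
| 2.4 | Day 8-10; no ultrasound | Day 14-16; endometrial and ovarian ultrasound |
| 4.3.3 | Day 8-10; four items, no ultrasound | Day 14-16; ultrasound is the only item |
| 5.7 | Endometrial and follicle measurements | Not mentioned |

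Sections 2.4 and 4.3.3 number the visits alike and leave screening unnumbered, so the visit named in 5.7 cannot be the day 14-16 visit under another count. If 5.7 meant an additional scan, both procedure lists would omit it and 5.7 would be silent on the scan that both lists require. Either way the text needs correcting. I do not rely on the grid in section 5.9, because its columns are shifted in the text available to me.

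Gap between the windows: smallest 14 − 10 = 4 days; largest 16 − 8 = 8 days.

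**Bias from the baseline.** Screening precedes randomization at Visit 1, so variation in the cycle day of the screening scan is independent of arm. The arm comparison is not biased.

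**Precision.** The documents give no standard deviations and no correlation between the two scans, so the loss from a raw change score cannot be calculated. The cost of adjusting can be bounded without those values.

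- Inputs: 36 women, three arms, 18 with and 18 without fibroids (sections 2.2 and 2.4), hence a 3 × 2 layout.
- Error degrees of freedom: 36 − 6 = 30; with one covariate, 29.
- Let rho be the within-cell correlation between the screening and Visit 3 values, and r = SD(screening)/SD(Visit 3).

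Variance of an arm difference, relative to the raw Visit 3 comparison:

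- Raw Visit 3 value: 1.
- Raw change: 1 + r² − 2·rho·r = (1 − rho²) + (r − rho)².
- Visit 3 value adjusted for screening, in expectation: (1 − rho²) × (1 + 1/(30 − 2)) = (1 − rho²) × 29/28.

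Both raw comparisons are at least 1 − rho². The adjusted one is therefore at most 29/28 = 1.036 times either, for any rho and r. In the worst case the 95% interval is sqrt(29/28) × 2.045/2.042 = 1.019 times as wide, about 2%.

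Illustration with r = 1 (the rho values are assumed, not taken from the documents):

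| rho | Raw Visit 3 | Raw change | Adjusted |
|---|---|---|---|
| 0 | 1 | 2.00 | 1.036 |
| 0.5 | 1 | 1.00 | 0.777 |
| 0.8 | 1 | 0.40 | 0.373 |
| 0.95 | 1 | 0.10 | 0.101 |

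Break-even points:

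- Against raw Visit 3, (1 − rho²) × 29/28 = 1 gives |rho| = sqrt(1/29) = 0.19.
- Against raw change at r = 1, 2(1 − rho) = (1 − rho²) × 29/28 gives rho = 27/29 = 0.93.

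A simulation with six women per cell, 20,000 trials per setting, rho from 0 to 0.95 and r of 0.5, 1 and 1.5 agreed. The largest ratio to the better raw comparison was 1.038, against the theoretical 1.036.

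**The case against.** The strongest reply is that this is a one-word slip with an obvious correct reading. Two schedules agree on Visit 3, and in section 4.3.3 the scan is the only reason to hold that visit. To lose the day 14-16 scan, a site would have to ignore both schedules and run a visit with no procedure. An extra Visit 2 scan, or a query to the coordinating center, is more likely. This stands as a judgment of likelihood. It does not remove the error: 5.7 is operational text, nothing in the documents reconciles it with the schedules, and the harm is claimed only for a site that follows it.

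The covariate advice can be called a preference. The plan expects to be underpowered for formal inference and already presents change descriptively. The 1.036 bound prices the remedy and does not show that the current plan loses anything. If the correlation is below 0.19, which is plausible with an uncontrolled cycle day, adjustment is slightly less precise than the raw Visit 3 comparison. The bound also assumes balance, and section 5.5 stratifies by age as well with varying block sizes, so six per cell is not guaranteed. All of this is fair, and it is why the point is secondary. But the plan does specify an ANOVA for comparison, and adding a baseline already collected has a small, known worst case.

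**Conclusion.** The concern holds. The visit in section 5.7 is wrong: a site that acts on it would scan 4 to 8 cycle days before the window in sections 2.4 and 4.3.3. This conclusion rests only on the text of the three sections.

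The baseline point is smaller. There is no bias between arms; there may be a loss of precision that the documents do not allow to be sized, and within-arm change is hard to interpret. The bound on the remedy (at most 3.6% more variance than either raw comparison) assumes bivariate normal values, a common slope across cells, balanced cells and both scans in all 36 women.

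The correction should be made, but it touches one secondary, mainly descriptive outcome.

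**What to change.** 1. In section 5.7, change the visit for the follow-up measurements to Visit 3 (day 14-16).
2. In sections 2.7 and 6.4, state that the arms will be compared on the Visit 3 value, with the screening value added as a covariate to the planned two-way ANOVA.
3. Keep raw change from screening as a descriptive summary, shown with the cycle day of the screening scan where available.

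The cost is one corrected visit number and one of about 30 error degrees of freedom. One data field may have to be added, because the documents do not show that cycle day is recorded for scans done up to three months earlier. No extra visit, scan or participant is needed.

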## 5.8 Laboratory Exam

Lab tests are found in Table 1 below. Both local and central labs will be utilized. The EGCG and metabolite analyses will be conducted in the lab of [name] at the University of Illinois. [name] is the pharmacokinetics core leader for UICentre, the academic drug discovery initiative at the University of Illinois at Chicago.

**Table 1. Screening labs of study women**

LOCAL LABORATORY BLOOD TESTS	CENTRAL LABORATORY BLOOD TESTS
FRIEND PK PRE-FRIEND PROTOCOL V. 2.1 JUNE 29, 2021	

Hormones	Liver	EGCG and metabolites
Estrogen	Total Bilirubin	EGCG
	ALT/AST	EGC
	Alkaline Phosphatase	ECG
		4'-O-methyl-epigallocatechin
		Genetic polymorphisms related to folate metabolism

## 5.9 Schedule of Evaluations

Study procedure	Cycle 1					Cycle 2				
	Screening	Visit 1 (Day 1 -5)	Visit 2 (Day 8 -10)	Visit 3 (Day 14-16)	Visit 4 (Day 30 - 35)	Visit 5 (Day 36-42)	Visit 6 (Day 43-49)	Visit 7 (Day 50-56)	Visit 8 (Day 57-63)	Visit 9 (Day 64-70)
Informed consent	X									
Inclusion/exclusion criteria	X									
Demographic information	X									
Medical history	X									
Concomitant medications	X	X	X						X	
Gynecological history	X									
Menstrual history	X									
Vital signs and weight	X	X	X						X	
Height	X									
Hip and abdominal circumference	X									X
Physical examination	X									
Pap smear	X*									
Pelvic and breast exam	X**									
Genetics sample, laboratory test	X									
Pelvic ultrasound	X †						X			
EGCG levels and metabolites, laboratory test	X	X	X						X	
Liver function, laboratory test	X	X	X						X	
Folate, laboratory test	X								X	
Estrogen levels, laboratory test	X	X	X							X
Contraceptive counseling	X	X	X							
Dispense EGCG	X									
Pill counts of EGCG		X	X						X	
Randomization and dispensation of clomiphene citrate or letrozole			X							

Pill counts of clomiphene citrate and letrozole			X		
Urine pregnancy test	X	X	X		X

\*If necessary per ACOG guidelines

\*\*if not done within past 12 months

† if not done within past 3 months

## 6 Data Analysis

### 6.1 Data Analysis

Data will be collected prospectively by designated research personnel at each study site, supervised by the site PI. Individual data will be entered into a web-based data management system created by the DCC, using only a study ID number.

### 6.2 Primary Outcome Measurements

The primary outcome parameter will be differences in pharmacokinetic parameters of EGCG and 2 of the major metabolites between the 3 treatment groups.

### 6.3 Secondary Outcome Measurements

The secondary outcome parameters will include:

- Changes in liver function between the 3 groups.
- Changes in estrogen levels (E2) between the 3 groups.
- Changes in endometrial thickness and ovarian characteristics between the 3 groups.
- Change in the pharmacokinetic parameters of EGCG and metabolites within each group.

### 6.4 Difference in serum folate levels among wildtype MTHFR, MTHFR (C677T), and MTHFR (A1298C) patients. Statistical Analyses

Since the number of patients for this study is minimal and multiple factors are of concern, descriptive statistics will be used, and the study is expected to be under powered to perform any formal statistical inference. The number, mean, standard deviation, median, interquartile range of the level of the pharmacokinetic parameters of EGCG and 2 of the major metabolites at different time points and the difference from screening to Visit 1 or Visit 2 or Visit 4, and the changes in liver function, hormone levels, endometrial thickness and follicular measurements will be presented for the three treatment groups, and then stratified by age group and/or the presence or absence of uterine fibroid. Patients with a detectable EGCG level at the screening visit will be excluded. For comparison, a two-way ANOVA will be used to compare the effects of the three treatments and the presence of fibroids on the above outcome parameters. With a sample size of 36 patients for the three treatment groups, and 18 subjects with uterine fibroids and 18 without uterine fibroids, with an alpha of 0.05, the power of the study would be 0.44 and 0.85 for a medium (0.25) or large (0.4) effect size, respectively. There are insufficient preliminary data in the literature to support or not support the reasonableness of these effect sizes. For the comparison of serum folate levels among wildtype MTHFR, MTHFR (C677T), and MTHFR (A1298C) patients, ANOVA (unadjusted) and multivariate linear regression will be used.

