### 5.2 Rationale for Design

The pharmacokinetics and hepatic safety of EGCG with clomiphene citrate and letrozole are unknown. A 3-arm study will be conducted in women with and without fibroids to allow comparisons between these groups. The results of this study will be used to confirm hepatic safety for the larger multi-center FRIEND study. The pharmacokinetics and hepatic safety of EGCG with clomiphene citrate and letrozole are unknown. A 3-arm study will be conducted in women with and without fibroids to allow comparisons between these groups. The results of this study will be used to confirm hepatic safety for the larger multi-center FRIEND study.

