## 5.5 Randomization/Treatment Initiation

Thirty-six (36) patients will be equally randomized via computer-generated randomization schedule to receive: 1) 800 mg of decaffeinated EGCG taken orally on a daily basis with food for up to 2 months; 2) 800 mg of decaffeinated EGCG taken orally on a daily basis with food for up to 2 months with clomiphene citrate 100mg for 5 days; 3) 800 mg of decaffeinated EGCG taken orally on a daily basis with food for up to 2 months with letrozole 5mg for 5 days.

Treatment assignments will be randomized for age groups and presence of fibroids by a varying-block-size design. The DCC statisticians will generate the randomization scheme for the study.

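### The PK comparison model has no body-size term, so the non-randomized fibroid contrast may be confounded by weight and the treatment contrast may lose some precision

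*Combined protocol and SAP*

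**What the plan says.** **Dose.** Section 5.5 gives all three arms "800 mg of decaffeinated EGCG taken orally on a daily basis with food for up to 2 months", and section 4.3.2 gives them the same number of capsules. Nothing is scaled to weight. (Sections 4.3.2 and 7.1 describe capsule content differently and must be reconciled, but the amount is common to all women either way.)

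**Body size.** The screening list in section 4.3.3 includes "Vital signs, height, weight, hip and abdominal circumference, BMI". EGCG is first dispensed at that visit. Weight is taken again at Visits 1, 2 and 4. The eligibility criteria in 4.3.4 and 4.3.5 set no weight or BMI limit.

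**Fibroid comparison.** Section 5.2 states: "A 3-arm study will be conducted in women with and without fibroids to allow comparisons between these groups". Section 4.1 sets the aim in women with and without fibroids. Women are recruited as 18 with and 18 without.

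**Primary outcome.** Section 6.2: "The primary outcome parameter will be differences in pharmacokinetic parameters of EGCG and 2 of the major metabolites between the 3 treatment groups".

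**Model.** Section 6.4, like 2.7, says that "a two-way ANOVA will be used to compare the effects of the three treatments and the presence of fibroids on the above outcome parameters". Descriptive tables are split by age group and fibroids. The only regression planned is for folate by MTHFR genotype, and its covariates are not named. No weight covariate, weight-normalised PK parameter or weight stratum appears anywhere.

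**The concern.** The model has two factors of different kinds. Treatment is randomized, so arms differ in weight only by chance. Fibroid status is a characteristic the women bring with them. Stratifying the randomization by age group and fibroids balances the treatment arms within those strata; it does nothing to balance weight between the fibroid groups.

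If weight differs by fibroid status, and exposure at a fixed amount depends on weight, the fibroid row of the ANOVA absorbs the weight difference and reports it as a fibroid effect. Comparing women by fibroid status is a stated purpose of the design, so a reader of the results would take that row seriously.

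Nothing else in the plan removes the problem. The planned differences from screening do not help for EGCG: a woman with a detectable screening level is excluded, so the difference is essentially the on-treatment level and keeps all between-woman variation. Adjusting for the Visit 1 profile would not rescue the fibroid question either, because that profile is taken on EGCG and would already contain any fibroid effect.

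For the treatment contrast the stake is smaller. Variance explained by weight stays in the error term, in a trial of only 36 women.

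**Working it through.** **1. The plan's own power figure.** Section 6.4 says that "with an alpha of 0.05, the power of the study would be 0.44 and 0.85 for a medium (0.25) or large (0.4) effect size". Inputs: "With a sample size of 36 patients for the three treatment groups, and 18 subjects with uterine fibroids and 18 without uterine fibroids"; equal allocation (5.5), so 12 per arm and 6 per treatment-by-fibroid cell.

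Noncentral F with λ = N·f² gives 36 × 0.25² = 2.25 and 36 × 0.40² = 5.76. On 2 and 30 df, power for treatment is 0.229 and 0.521; for fibroids (1 and 30 df) it is 0.306 and 0.642. The stated pair is not reproduced at N = 36. It matches the treatment effect at N = 72 (2 and 66 df: 0.443 and 0.853). A repeated-measures version (3 groups, 4 measures, correlation 0.3) also comes close (0.445 and 0.854), but no such model is described. This is a separate problem; here 0.229 and 0.521 serve as the baseline.

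**2. Possible bias in the fibroid contrast.** The documents give no weight distribution, no weight difference by fibroid status and no weight-exposure relation, so all inputs are assumptions. Take a comparison mean of 70 kg, a fibroid-group mean d kg higher, and exposure proportional to weight^(-b). The spurious exposure ratio is (70/(70 + d))^b.

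| d | b = 0 | b = 0.25 | b = 0.75 | b = 1 |
|---|---|---|---|---|
| 0 kg | 1 | 1 | 1 | 1 |
| 5 kg | 1 | 0.983 | 0.950 | 0.933 |
| 15 kg | 1 | 0.953 | 0.864 | 0.824 |

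If the fibroid group were lighter, the ratio would exceed 1.

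**3. What that does to the 5% fibroid test.** With log-scale SD σ = √ln(1 + CV²), the bias in SD units is b·ln(1 + relative weight difference)/σ. For CV 50%, σ = √ln 1.25 = 0.472; for CV 30%, σ = √ln 1.09 = 0.294. A 10% difference with b = 0.75 gives 0.75 × 0.0953 = 0.0715, or 0.151 SD at CV 50% and 0.244 SD at CV 30%. A 20% difference with b = 1 gives 0.1823, or 0.386 and 0.621 SD. Half of each is the effect size f in a test on 1 and 30 df. With no true fibroid effect, the test rejects 7% to 20% of the time at CV 50% and 11% to 44% at CV 30%. With equal weights it stays at 5%.

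**4. Precision of the treatment contrast.** Let R² be the share of within-cell log-PK variance explained by log weight (assumed). A 3×2 model with interaction has 36 - 6 = 30 residual df, and one covariate leaves 29. The approximate ratio of adjusted to unadjusted SE is √((1 - R²) × 30/29). Equivalent sample size is 36 divided by the square of that ratio. Adjusted power uses λ = 36·f²/(1 - R²) on 2 and 29 df.

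| R² | SE ratio | Equivalent n | Power at f = 0.25 | Power at f = 0.40 |
|---|---|---|---|---|
| no covariate | 1 | 36 | 0.229 | 0.521 |
| 0 | 1.017 | 34.8 | 0.228 | 0.520 |
| 0.1 | 0.965 | 38.7 | 0.250 | 0.566 |
| 0.2 | 0.910 | 43.5 | 0.277 | 0.620 |
| 0.3 | 0.851 | 49.7 | 0.312 | 0.682 |

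Break-even for the SE is 1 - 29/30 = 0.033. The plan does not say whether the interaction is fitted; without it there are 32 residual df and the break-even is 1/32 = 0.031.

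**5. With age group added as well.** Two terms leave 28 df, and the ratio becomes √((1 - R²) × 30/28), with R² now the joint share: 1.035, 0.982, 0.926 and 0.866 at R² = 0, 0.1, 0.2 and 0.3. Break-even is 1 - 28/30 = 0.067.

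**The case against.** Most of the case against is a case for restraint, and much of it stands.

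- A reader might infer that the fibroid comparison is confounded by weight. The documents do not support that. It needs weight to differ by fibroid status and weight to affect EGCG exposure, and neither is shown. Eligibility also asks for healthy women without chronic disease; whether that narrows the weight range is not stated.
- A reader might infer that the primary outcome is biased. It is not. Section 6.2 defines it between randomized arms, and no secondary outcome in 6.3 is a fibroid contrast. The fibroid comparison rests on the design rationale (5.2), the aim (4.1) and the ANOVA itself.
- A reader might infer that the plan treats fibroid status as if it were randomized. A two-way ANOVA makes no such claim, and the protocol consistently presents fibroids as a recruitment category and stratification factor. The fair criticism is only that it uses the same effects wording for both factors, with no caution about the second.
- The plan calls itself descriptive and underpowered, which lowers the impact. It still commits to a model, an alpha and a power figure, so the model deserves to be sound.
- The precision gain is modest. For the treatment contrast, the Visit 1 profile, taken when the second drug is first dispensed, might carry much of the same between-woman variation; what weight would add beyond it is unknown.
- Adjusting for weight alone would be incomplete. Age group is a stratification factor, is absent from the ANOVA, and may also differ by fibroid status.

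**Conclusion.** The point holds in conditional form. The EGCG amount is fixed, weight is measured before treatment, the PK model has no body-size term, and an intended comparison is non-randomized. That comparison may be confounded by weight, and the plan has no adjustment for it.

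The bias runs from none (equal mean weights, or no weight effect on exposure) to a spurious ratio of about 0.98 to 0.82 under the assumed 5 to 15 kg differences from 70 kg and exponents 0.25 to 1. The randomized treatment contrast is unbiased. Its standard error would change by +1.7% to -15% for an R² of 0 to 0.3 with weight alone, and even at R² = 0.3 power at f = 0.40 reaches only 0.68. Better precision is therefore a side benefit. The main reason to act is that the fibroid result cannot otherwise be interpreted.

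**What to change.** In sections 2.7 and 6.4:

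- Analyse log-transformed EGCG and metabolite PK parameters with treatment, fibroid status, log screening weight and age group, and state whether the treatment-by-fibroid interaction is included.
- Tabulate screening weight by fibroid group.
- Report adjusted and unadjusted fibroid ratios side by side, each with a 95% CI.
- Label the fibroid contrast observational, so that neither ratio is read as an effect secured by the design.

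**Cost.** No new data are needed; the covariates cost one residual df each. If weight explains less than about 3% of PK variance, there is a slight loss of precision (1.7% at worst in the approximation for weight alone, 3.5% with age group as well if neither explains anything). If weight does differ by fibroid status, the adjusted fibroid interval may be wider than the unadjusted one, which reflects how hard the two are to separate in 36 women.
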